# PROTOCOL SYNOPSIS

Protocol Title:	Urea for chronic hyponatremia: a pilot study			
Protocol Number:	STUDY20050035			
NCT Number:	NCT04588207			
Version # and Date:	Version #13. 8/25/22			
Clinical Phase:	2			
Investigational Drugs:	Urea			
Trial Site:	University of Pittsburgh Medical Center			
IND Sponsor:	[name]			
Investigator:	[name]			
Sub-Investigators:	[name] [name] [name] [name]			
Study Monitor:	DSMB			
Research Facilities:	
 
UPMC Kidney Clinic
 
University of Pittsburgh Neuromuscular Research Laboratory
 
UPMC Montefiore Clinical and Translational Research
 
			
Clinical Laboratories:	UPMC Presbyterian (Falk Medical Building) UPMC Magee-Womens UPMC Shadyside UPMC Mercy UPMC Passavant UPMC East UPMC St Margaret UPMC McKeesport			
Study Rationale:	Hyponatremia, defined as a plasma sodium concentration (PNa) <135 mmol/L, is the most common electrolyte disorder encountered clinically. Hyponatremia is categorized as mild (i.e., PNa 130-134 mmol/L), moderate (i.e., PNa 120-129 mmol/L), or severe (i.e., PNa<120 mmol/L) and as acute (i.e., duration <48 hours), or chronic (i.e., duration ≥48 hours). The small proportion of patients with this disorder who present with severe and/or acute hyponatremia frequently have overt neurological symptoms and require hospitalization and urgent treatment. Much more commonly, patients with this condition have chronic non-severe hyponatremia that does not typically require hospitalization or urgent therapy. While such patients are seemingly asymptomatic, a growing body of evidence demonstrates that even mild chronic hyponatremia is associated with subtle neurocognitive deficits, gait and postural disturbances, development of osteoporosis, heightened risk for			

	falls and fractures, and increased mortality. As a result, there has been substantial interest in identifying treatments that can be used for the long-term management of patients with chronic hyponatremia that are safe, well tolerated, and that mitigate the morbidity and mortality associated with this condition. The most common etiology of chronic hyponatremia is the syndrome of inappropriate antidiuretic hormone secretion (SIADH), and interventions currently used to treat this condition are based on our understanding of its pathophysiology. However, some of these treatments, including loop diuretics, oral sodium chloride tablets, and fluid restriction lack evidence of efficacy from clinical trials, and in the case of fluid restriction, pose significant challenges to long-term patient compliance. Other therapies such as vasopressin receptor antagonists (i.e., vaptans) have been shown to improve PNa in clinical trials, yet their widespread use is limited by the notable risk for serious side effects, including liver injury, as well as very high costs. Consequently, at present, there are no treatment interventions available that have been shown in clinical trials to be efficacious, safe, easy for patients to adhere to, and affordable for long-term use. Small case series conducted in Europe have investigated the efficacy of increasing urinary solute excretion through the administration of oral urea, and found this agent to be safe and				
	effective for the treatment of chronic hyponatremia. However, these studies were not designed or powered to examine the effect of long-term urea therapy on key patient-centered clinical outcomes. Moreover, urea has not been available for clinical use in the United States until recently when a novel commercial formulation was introduced. In the first published study of this novel formulation of urea, our group reported it to be effective, safe, and well tolerated for the treatment of inpatient hyponatremia. However, these findings were derived from a retrospective cohort study that focused exclusively on short-term inpatient use of urea in a small number of patients. To date, there have been no clinical trials that have investigated the efficacy and safety of oral urea for the treatment of chronic hyponatremia.				
Study Objectives	Primary				
Study Objectives.	
 
To determine the number and proportion of patients with chronic hyponatremia due to SIADH who met inclusion/exclusion criteria and were enrolled in the study.
 
To determine the number and proportion of enrolled patients with chronic hyponatremia due to SIADH who completed the study.
 
				
	
 
To determine the monthly enrollment rate of patients with chronic hyponatremia due to SIADH who met inclusion/exclusion criteria.
 
				

4.	To determine the number of prescribed urea doses
	taken by patients with chronic hyponatremia due to
	SIADH at completion of the study.
5.	To determine the reasons for non-adherence to urea
	therapy by patients with chronic hyponatremia due to
	SIADH.
6	To assess the change in percentage accuracy action
•	boundary selection in patients with chronic
	hypopatremia due to SIADH from baseline to day 42 of
	uroa thorany
7	To appear the change in overall score of concerimeter
1.	ability better in retients with abranic hyperetromic due
	ability battery in patients with chronic hyponatremia due
•	to SIADH from baseline to day 42 of urea therapy.
8.	To assess the change in the sample entropy of the
	center of pressure data from the force plate in patients
	with chronic hyponatremia due to SIADH from baseline
	to day 42 of urea therapy.
9.	To assess the change in percentage angular deviation
	of vestibular control system using dynamic
	representation of upright stance in patients with chronic
	hyponatremia from SIADH from baseline to day 42 of
	urea therapy.
10.	To assess the change in percentage angular deviation
	of somatosensory control system using dynamic
	representation of upright stance in patients with chronic
	hyponatremia due to SIADH from baseline to day 42 of
	urea therapy.
11.	To assess the change in percentage angular deviation
	of visual control system using dynamic representation
	of upright stance in patients with chronic hyponatremia
	due to SIADH from baseline to day 42 of urea therapy.
12	To assess the change in percentage weight symmetry
	using dynamic representation of upright stance in
	natients with chronic hyponatremia due to SIADH from
	baseline to day 12 of urea therapy
13	To assess the change in movement latency of nosture
10.	control and stability using dynamic representation of
	upright stance in patients with chronic hypopatremia
	due to SIADH from baseline to day 42 of urea therapy
11	To assess the change in amplitude scaling of posture
14.	control and stability using dynamic representation of
	upright stance in patients with chronic hyperatromia
	due to SIADH from baseling to day 42 of urga therapy
15	To determine the number and properties of petients
15.	with abrania hyperastromia due to SIADU encelled in the
	with children avents related to the use of the
40	Suuy will adverse events related to the use of drea
10.	i o determine the presence and nature of adverse
	events in patients with chronic hyponatremia due to
	SIADH related to urea therapy.
secon	uary

	1.	To determine the number of patients screened for the
		study.
	2.	To determine the number and proportion of patient
		screened who met inclusion/exclusion criteria for the
		study.
	3.	To determine the number and proportion of patients
		enrolled in the study who took more than 80% of
		prescribed urea doses.
	4.	I o determine the number and proportion of patients
	F	enrolled in the study who thought urea was acceptable.
	Э.	
	6	To assess the change in SE 12 (Health Survey) Mental
	0.	Component Summary (MCS) in patients with chronic
		hyponatremia due to SIADH from baseline to day 42 of
		urea therapy
	7.	To assess the change in SF-12 (Health Survey)
		Physical Component Summary (PCS) in patients with
		chronic hyponatremia due to SIADH from baseline to
		day 42 of urea therapy.
Study Hypothesis:	1.	We hypothesize that we will be able to recruit at least
otady Hypothesis.		10% of eligible patients with chronic hyponatremia due
	-	to SIADH.
	2.	We hypothesize that we will be able to document at
		least 80% compliance with prescribed urea doses in
	2	patients with chronic hyponatremia due to SIADH.
	э.	ve hypothesize that the will significantly increase the
		the baseline level in patients with chronic hypopatremia
		due to SIADH
	4.	We hypothesize that urea will significantly improve the
		scores on neurocognitive and posture control and
		stability assessments at day 42 compared with the
		baseline scores in patients with chronic hyponatremia
		due to SIADH.
	5.	We hypothesize that adverse events related to the use
		of urea in patients with chronic hyponatremia due to
	-	SIADH will be very uncommon.
Study Aims:	1.	To assess the feasibility of recruiting patients with
-		urea and to evaluate their adherence to oral urea
	2	To assess the effect of oral urea on plasma sodium
	۷.	concentration and on neurocognitive function and
		postural control and stability in patients with chronic
		hyponatremia due to SIADH.
	3.	To explore the safety of oral urea in patients with
		chronic hyponatremia due to SIADH.
Study Design:	The pr	oposed pilot study is designed as a prospective, cross-
Clady Design.	over tr	ial. Over a 13.5-month period, we will recruit 30

	outpatients with chronic non-severe hyponatremia (PNa 125 to 132 mmol/L) confirmed to be due to SIADH. Following enrollment, patients will be randomly assigned on 1:1 ratio to one of two sequence groups. Patients assigned to group "Urea ON, then Urea OFF" will receive oral urea for 42 ± 3 days (period 1), followed by a 10 ± 4-day period in which patients will be off urea (washout period). Patients then will be off urea for 42 ± 3 days (period 2). Patients assigned to group "Urea OFF, then Urea ON" will be off urea therapy for 42 ± 3 days (period 1), and following a 10 ± 4-day washout period then they will initiate urea for 42 ± 3 days (period 2). Patients will have PNa assessed at baseline and on days 7 ± 2, 14 ± 2, and 42 ± 3 during periods 1 and 2 of the study and will undergo neurocognitive and postural control and stability testing on days 0 and 42 of each of the study periods. All patients will be advised to restrict their fluid intake to ≤1.2 liters during periods 1 and 2			
Planned Sample Size:	30 patients			
Duration of Treatment:	42 ± 3 days			
Major Inclusion Criteria:	
 
Age ≥18 years
 
Attended ≥1 visit at a UPMC outpatient clinic within the prior 12 months
 
Chronic hyponatremia with a history of ≥ 2 sequential plasma sodium concentration (PNa) between 125 mmol/L and 132 mmol/L performed ≥ 14 days apart within the last 18 months with most recent PNa ≤ 132 mmol/L prior to screening
 
Patients are ambulatory without the need for any assist device (e.g., cane, walker)
 
Mini-mental state examination (MMSE) score ≥ 25
 
Diagnosis of SIADH established by the Bartter and Schwartz criteria as follows:         
 
a. Hyponatremia with a PNa between 125 mmol/L and 132 mmol/L
 
b. Plasma osmolality < 275 mOsm/kg
 
c. Clinical euvolemia
 
d. Urine osmolality > 100 mosm/kg
 
e. Urine Na ≥ 20 mmol/L
 
f. Intact adrenal function (i.e., morning plasma cortisol value ≥15 µg/dL, or negative corticotropin stimulation test)
 
g. Normal thyroid stimulating hormone level (i.e., TSH between 0.3 to 5 µIU/mL)
 
h. eGFR ≥ 45 ml/min/1.73 m2)
 
 
 
Nephrology patients who meet eligibility for the study including a nadir serum sodium of no less than125 mmol/L and have already started urea and treating physician agrees to discontinuing prescribed urea.
 
			

	1 Cirrhosis and/or end-stage liver disease
Major Exclusion	2 Heart failure on divisities and/or with recorded left
Criteria:	2. Redit failule of differences and/of with recorded left
	3. Chronic kidney disease with most recent estimated
	glomerular filtration rate < 45 ml/min/1.73m2
	4. Adrenal insufficiency
	5. Untreated hypothyroidism
	6. Urinary tract obstruction within the prior 2 months
	7. Uncontrolled hyperglycemia (most recent random
	plasma dlucose $\geq 200 \text{ mg/dL}$
	8 Ongoing drug treatment for hyponatremia with vantans
	or combination of loop diviretics and salt tablets
	9 Active malignancy (not on remission)
	10 Active infection
	11 Nourological disorders with impairment of ambulation
	and/or cognition
	12. End-stage lung disease with marked impairment in
	ambulatory capacity
	13. Chronic pain with impairment of ambulation and/or
	cognition
	14. Chronic nausea
	15. Hypersensitivity to urea
	16. Women who are pregnant, breast feeding, or of
	childbearing potential who are not using contraception
	17. Patient is unable to consent for himself/herself
	Primary Endpoints
Study Endpoints:	1 Number and proportion of patients who met
	inclusion/exclusion criteria and were enrolled in the
	study
	2 Number and properties of national encoded who
	2. Number and proportion of patients enfolied who
	2 Manthly annuline study
	3. Monthly enrollment rate
	4. Number of prescribed urea doses taken by patients
	5. Reasons for non-adherence to urea therapy
	6. Change in plasma sodium concentration
	7. Change in percentage accuracy action boundary
	9 Change in overall score of concerimeter ability bettery
	0. Change in the sample entrany of the center of pressure
	9. Change in the sample entropy of the center of pressure
	data from the force plate
	10. Change in percentage angular deviation of vestibular
	control system using dynamic representation of upright
	stance
	11. Change in percentage angular deviation of
	somatosensory control system using dynamic
	representation of upright stance
	12. Change in percentage angular deviation of visual
	control system using dynamic representation of upright
	atanaa
	stance
	13. Change in percentage weight symmetry using dynamic

 
14. Change in movement latency of posture control and stability using dynamic representation of upright stance
 
15. Change in amplitude scaling of posture control and stability using dynamic representation of upright stance
 
16. Number and proportion of patients enrolled in the study with adverse events related to the use of uses
 

17 Adverse events related to uree
Secondary Endpoints:
1. Number of patients screened

Number and proportion of patient screened who met

inclusion/exclusion criteria for the study

 
Number and proportion of patients who took more than 80% of prescribed urea doses
 

 
Number and proportion of patients who thought the medication was acceptable
 

5. Average ratings for medication acceptability

 
Change in SF-12 (Health Survey) Mental Component Summary (MCS)
 

 
Change in SF-12 (Health Survey) Physical Component Summary (PCS)
 

# 1. OBJECTIVE, SPECIFIC AIMS, BACKGROUND, AND SIGNIFICANCE

# **1.1 OBJECTIVE**

## **Primary:**

- a. To determine the number and proportion of patients with chronic hyponatremia due to SIADH who met inclusion/exclusion criteria and were enrolled in the study.
- b. To determine the number and proportion of enrolled patients with chronic hyponatremia due to SIADH who completed the study.
- c. To determine the monthly enrollment rate of patients with chronic hyponatremia due to SIADH who met inclusion/exclusion criteria.
- d. To determine the number of prescribed urea doses taken by patients with chronic hyponatremia due to SIADH at completion of the study.
- e. To determine the reasons for non-adherence to urea therapy by patients with chronic hyponatremia due to SIADH.
- f. To assess the change in percentage accuracy action boundary selection in patients with chronic hyponatremia due to SIADH from baseline to day 42 of urea therapy
- g. To assess the change in overall score of sensorimotor ability battery in patients with chronic hyponatremia due to SIADH from baseline to day 42 of urea therapy.
- h. To assess the change in the sample entropy of the center of pressure data from the force plate in patients with chronic hyponatremia due to SIADH from baseline to day 42 of urea therapy.
- i. To assess the change in percentage angular deviation of vestibular control system using dynamic representation of upright stance in patients with chronic hyponatremia from SIADH from baseline to day 42 of urea therapy.
- j. To assess the change in percentage angular deviation of somatosensory control system using dynamic representation of upright stance in patients with chronic hyponatremia due to SIADH from baseline to day 42 of urea therapy.

- k. To assess the change in percentage angular deviation of visual control system using dynamic representation of upright stance in patients with chronic hyponatremia due to SIADH from baseline to day 42 of urea therapy.
- I. To assess the change in percentage weight symmetry using dynamic representation of upright stance in patients with chronic hyponatremia due to SIADH from baseline to day 42 of urea therapy.
- m. To assess the change in movement latency of posture control and stability using dynamic representation of upright stance in patients with chronic hyponatremia due to SIADH from baseline to day 42 of urea therapy.
- n. To assess the change in amplitude scaling of posture control and stability using dynamic representation of upright stance in patients with chronic hyponatremia due to SIADH from baseline to day 42 of urea therapy
- o. To determine the number and proportion of patients with chronic hyponatremia due to SIADH enrolled in the study with adverse events related to the use of urea
- p. To determine the presence and nature of adverse events in patients with chronic hyponatremia due to SIADH related to urea therapy.

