## Secondary:

- a. To determine the number of patients screened for the study.
- b. To determine the number and proportion of patient screened who met inclusion/exclusion criteria for the study.
- c. To determine the number and proportion of patients enrolled in the study who took more than 80% of prescribed urea doses.
- d. To determine the number and proportion of patients enrolled in the study who thought urea was acceptable.
- e. To determine the patients' average ratings for urea acceptability.
- f. To assess the change in SF-12 (Health Survey) Mental Component Summary (MCS) in patients with chronic hyponatremia due to SIADH from baseline to day 42 of urea therapy.
- g. To assess the change in SF-12 (Health Survey) Physical Component Summary (PCS) in patients with chronic hyponatremia due to SIADH from baseline to day 42 of urea therapy.

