#### Intervention (oral urea) and study period 1:

Patients randomized to study group "Urea ON, then Urea OFF" (N=15) will begin 42 ± 3 days of urea therapy, while those randomized to study group "Urea OFF, then Urea ON" (N=15) will not receive urea during this period. All patients will be asked to restrict their fluid intake to  $\leq$ 1.2 L/day during period 1. We will provide participants with a protocol for recording their daily fluid intake which includes carefully measuring all ingested fluids with a measuring cup and recording them on a study diary during the entire study period. We will use the new American formulation of oral urea (i.e., Ure-NaTM), which is packaged as a powder that is mixed with 4 oz. of water for oral consumption. Group "Urea ON, then Urea OFF" patients will be given 48 powder pouches of Ure-Na (15 g of urea per pouch) and will be instructed to start at a dose of 15 g once daily. Dose titration will be based on the absolute increase in PNa on days 7 ± 2 and 14 ± 2 as follows:

- Day 7: If PNa increases ≥3 mmol/L from baseline, then continue same urea dose. If PNa increases <3 mmol/L from baseline, then increase urea to next dose.
- Day 14: If PNa increases ≥ 6 mmol/L from baseline, or PNa increases <6 mmol/L from baseline and PNa ≥135 mmol/ L, then continue same urea dose. If PNa increases <6 mmol/L from baseline and PNa <135 mmo/L, then increase urea to next dose.

The dosing scheme for urea will involve increasing when appropriate, from the starting dose of 15 g/day, to 30 g/day in 2 divided doses, and subsequently, when appropriate, from 30 g/day to 60 g/day (in 2 divided doses). The maximal dose of urea administered will be 60 g/day. Patients will undergo a PNa check approximately  $7 \pm 2$  days after a urea dose adjustment to less than the maximal dose of urea allowed. Patients will record the doses of urea they consume each day during treatment period 1 in the study diary.

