### 2.4 STUDY ENDPOINTS

### 2.5 STATISTICAL ANALYSIS

#### 2.5.1 Sample Size Determination

This pilot study aims to assess the feasibility of conducting a future clinical trial. Thus, the sample size of 30 patients was determined based on clinical and logistical reasons rather than statistical requirements. For Aim 1, we anticipate identifying approximately 300 potentially eligible patients during the 13.5 months of recruitment (~22 per month). A 95% confidence interval (CI) for the randomization rate provides a 3% margin of error (MoE) assuming the true rate was 10% (~3 per month). If the underlying dropout and adherence rates were 80%, a sample size of 30 provides 14% MoE for 95% CIs. For Aim 2, our sample size provides 83% power to detect a standardized mean difference of 0.65 for our efficacy outcomes. We are not powered to detect smaller effect sizes. However, since this is a proof-of-concept study, detecting a moderate-to-large effect size increases our confidence in the potential efficacy of urea. For Aim 3, underlying adverse events rates of 5% to 10%, 95% CIs will provide 8% to 11% MoE, respectively.

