## **10. WITHDRAWAL OF SUBJECTS AND STOPPING CRITERIA:**

Adverse Events: Oral urea use is occasionally associated with the onset of nausea, vomiting, diarrhea and headaches. If these symptoms appear then they will be initially managed by asking patients to monitor their symptoms and report to the research coordinator if symptoms persist after 24h. If symptoms persist, urea dose will be reduced by 50%. If symptoms persist 72h after reducing the dose of urea, urea will be discontinued. Participant will be asked to return remaining urea doses, and after consultation with all the members of the research team, participant will be formally withdrawn from the study. Data no longer will be collected from the withdrawn subject and subject will be referred to the UPMC kidney clinic for follow up. Subjects withdrawn from the study will be replaced using the regular procedures described for recruitment. We will continue recruitment until the target number of patients are enrolled.

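### The urea-related adverse event proportion is stated over all enrolled patients, so anyone who leaves before a first dose of urea can only lower it; the effect is modest and cheap to remove

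*Combined protocol and SAP*

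**What the plan says.** Section 1.1, primary objective (o), and endpoint 16 in the synopsis state the safety proportion over patients "enrolled in the study with adverse events related to the use of urea". Section 2.5.1 gives the Aim 3 precision as "underlying adverse events rates of 5% to 10%, 95% CIs will provide 8% to 11% MoE". Section 2.5.4 restricts event reporting to time on urea but names no denominator, and no safety or treated population is defined.

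Section 2.1 puts the Urea OFF, then Urea ON group through a 42 ± 3-day period and a 10 ± 4-day washout before urea begins. Section 2.2 says of that group in period 1: "N=15) will not receive urea during this period".

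On adherence, primary objective (d) is "To determine the number of prescribed urea doses taken by patients with chronic hyponatremia due to SIADH at completion of the study", and secondary objective (c) counts patients "enrolled in the study who took more than 80% of prescribed urea doses". The term prescribed is not defined. Section 10 lets the team change the prescription for persistent symptoms, first by a reduction and then: "If symptoms persist 72h after reducing the dose of urea, urea will be discontinued". That patient is withdrawn, data collection ends, and a replacement is recruited. Section 2.3.6 does not withdraw patients for failing to take urea. Neither section says how withdrawn and replacement patients enter any denominator.

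**The concern.** A drug-related event rate should be read among people who took the drug. Here half the patients wait several weeks before exposure, and each one lost in that interval adds to the denominator with no chance of adding to the numerator. The error runs in one direction, towards hypothesis (e) in Section 1.2, that urea-related events will be very uncommon. The rate is one of the primary outputs meant to inform a larger trial.

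Adherence raises a related but weaker question. The protocol itself can lower or end the prescription, so doses taken over doses prescribed has more than one meaning, and Section 1.2 sets an 80% target on it.

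**Working it through.** **Inputs.** 30 patients, 15 per sequence (Sections 2.1 and 2.2); event rates of 5% and 10% (Section 2.5.1); treatment for 42 days (Section 2.3.4). The plan gives no forecast of how many leave before a first dose. Section 2.5.1 says "If the underlying dropout and adherence rates were 80%, a sample size of 30 provides 14% MoE for 95% CIs". I read this as 80% retention, so 20% loss; that reading is an assumption. Twenty per cent of the 15 OFF-first patients is 3. I show 1 to 3, with 6 (20% of all 30, every one leaving before urea) as an extreme. I take enrolled to mean the 30 randomised patients.

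**Time before exposure.** 42 + 10 = 52 days, with a range of 39 + 6 = 45 to 45 + 14 = 59.

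**The plan's own margins.** Half-width = 1.96 × √(p(1 − p)/n), n = 30:
- p = 0.05: 7.8%, stated as 8%.
- p = 0.10: 10.7%, stated as 11%.
- p = 0.80: 14.3%, stated as 14%.

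The stated figures reproduce with all 30 patients.

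**Direction.** For x affected patients, x/enrolled = (x/treated) × (treated/enrolled). The second factor is at most 1, so the enrolled proportion cannot exceed the treated one.

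**Size, with 3 affected patients (illustrative).**

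| Never treated | Treated | Over 30 enrolled | Over treated | Margin at 5% | Margin at 10% |
|---|---|---|---|---|---|
| 0 | 30 | 10.0% | 10.0% | 7.8% | 10.7% |
| 1 | 29 | 10.0% | 10.3% | 7.9% | 10.9% |
| 2 | 28 | 10.0% | 10.7% | 8.1% | 11.1% |
| 3 | 27 | 10.0% | 11.1% | 8.2% | 11.3% |
| 6 | 24 | 10.0% | 12.5% | 8.7% | 12.0% |

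Exact 95% intervals: 3/30, 2.1% to 26.5%; 3/27, 2.4% to 29.2%.

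**With replacement.** If 3 never-treated patients are replaced and all stay in the count, enrolled is 33 and treated is 30: 3/33 = 9.1% against 3/30 = 10.0%. The direction is unchanged.

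**Adherence.** Take a patient who takes every dose and is stopped on day 10. If prescribed doses end at the stop, he scores 100%. Against the planned course he has 10/42 = 24% of days. Stops on days 5, 14 and 21 give 12%, 33% and 50%. The text does not choose between these readings.

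The enrolled denominator in secondary objective (c) can work the other way. If 80% of treated patients are adherent and never-treated patients count as not adherent, then 1, 2 or 3 never treated give 0.80 × 29/30 = 77%, 0.80 × 28/30 = 75% and 0.80 × 27/30 = 72%.

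**The case against.** The strongest reply on the event rate is that the effect is small. A shift of at most 1.1 points for up to 3 never-treated patients sits well inside an 11-point margin. With 27 to 29 treated, the margins still round to the stated 8% and 11%. Replacement may bring the number treated close to 30, so margins computed at 30 do not show that unexposed patients were counted. Endpoint 16 also reports the number of patients, so a reader who knew how many were treated could recompute the rate. All of this stands as to size. None of it gives a reason to keep never-treated patients in the denominator.

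A reader might go further and infer that the adherence measure also flatters urea, because doses cease to be prescribed once urea is stopped for intolerance. The documents do not support that. No section says when doses stop counting, and primary objective (d), tied to study completion, could as easily leave the withdrawn patient out. The enrolled denominator in secondary objective (c) can lower adherence. Nor is intolerance hidden: a patient stopped for symptoms is a non-completer under primary objective (b), and the events count under (o) and (p). What remains is an undefined term.

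**Conclusion.** The event-rate point holds on the text. The denominator in objective (o) and endpoint 16 includes patients who may never be exposed, and it can only pull the urea-related proportion down. The size is modest: 10.0% against 10.3% to 11.1% with 3 affected patients and 1 to 3 never treated, and 12.5% in the extreme of 6. These counts are assumptions. If everyone takes at least one dose, the two figures agree.

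On adherence, the supported conclusion is only that the denominator is undefined, as is the handling of withdrawn and replacement patients. The direction of any effect depends on a reading that the plan does not fix.

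**What to change.** 1. Reword primary objective (o), its counterpart in the synopsis, and endpoint 16 as the number and proportion of patients who took at least one dose of study urea and had a urea-related event. State that treated patients who are later withdrawn or replaced stay in both numerator and denominator. The words study urea matter because inclusion criterion (g) admits patients who took prescribed urea before the trial. Name the same set in Section 2.5.4.
2. In Section 2.5.1, give the Aim 3 margin for the number expected to be treated, for example about 8.2% and 11.3% at 27.
3. As a lesser clarification, define adherence for every patient who starts urea with two figures side by side: doses taken over doses due under the prescription in force on each day; and days on urea out of the planned 42, with days after any discontinuation counted as not taken. Say how withdrawn and replacement patients are counted.

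The last dose level should not serve as the denominator for the whole course. A fully adherent patient titrated under Section 2.2, with 7 days at one pouch, 7 at two and 28 at four, takes 7 + 14 + 112 = 133 pouches. At the last level the denominator would be 42 × 4 = 168, giving 79%, so planned titration would be scored as non-adherence. A halved dose would shrink the denominator instead.

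The cost is wording. The study diaries and returned-pouch counts are already collected, and no clinical rule changes. The downside is that the reported event rate and its margin become slightly less favourable.
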